7.2 Unexpected Adverse Events

An unexpected adverse event is any event not associated by nature or intensity with the investigational agent(s) under study. A comprehensive list of adverse events and potential risks related to DUPILUMAB is provided in this Protocol and in the Consent form. The study agent may cause allergic reactions in very rare instances. A severe allergic reaction could be life-threatening. Examples of allergic reactions include: rash; shortness of breath; wheezing; sudden drop in blood pressure; swelling around the mouth, throat, or eyes; fast pulse; and sweating.

7.3 Serious Adverse Events and Serious Adverse Drug Reactions

The investigator must assess each event to determine if it meets the criteria for classification as a serious adverse event (SAE) or serious adverse drug reaction (ADR). An SAE/ADR is defined in the Code of Federal Regulations (21CFR312.32) as any event that:

- results in death
- is life-threatening
- results in inpatient hospitalization or prolongation of existing hospitalization
- results in persistent or significant disability or incapacity
- results in congenital anomaly or birth defect
- is medically significant in the opinion of the investigator

All SAEs that occur any time while a patient is on study (*i.e.*, as soon as the informed consent has been signed) or within 30 days of the last dose of study drug administration must be documented, regardless of the suspected relationship to the investigational agent(s). Any SAE occurring more than 30 days after the last dose of the study drug(s) must be recorded if a causal relationship to the investigational agent(s) is suspected.

7.3.1 Progression of malignancy

Progression of a patient's malignancy should *not* be considered an AE unless, in the investigator's opinion, study treatment resulted in an exacerbation of the patient's condition. If disease progression results in death or hospitalization while on study or within 30 days of the last dose of study drug administration, progressive disease will be considered an SAE.

7.3.2 Life-threatening events

A life-threatening event is any AE that places the patient at immediate risk of death from the reaction as it occurs. It is not a reaction that, had it occurred in a more severe form, might have caused death.

7.3.3 Hospitalization or prolongation of hospitalization

Hospitalization encompasses any inpatient admission (even if < 24 hours) resulting from a precipitating treatment-emergent adverse event. For chronic or long-term patients, inpatient admission also includes transfer within the hospital to an acute or intensive care inpatient unit. Hospitalizations for administrative reasons or a non-worsening preexisting condition should not be considered AEs (e.g., admission for workup of a persistent pretreatment laboratory abnormality, yearly physical exam, protocol-specified admission, or prostatectomy surgery).

Hospitalization because of an unplanned event will be deemed an SAE. Preplanned treatments or surgical procedures should be noted in the baseline documentation. In the case of this study, all patients will have a preplanned prostatectomy surgery.

Prolongation of hospitalization is any extension of an inpatient hospitalization beyond the stay anticipated or required for the original reason for admission.

7.3.4 Significant disability

This is defines as a substantial disruption of the patient's ability to conduct normal life functions and activities of daily living.

7.3.5 Congenital anomaly

If the female partner of a male patient becomes pregnant during the course of the study, the treating physician must be notified immediately. All confirmed pregnancies must be immediately reported to the principal investigator and the medical monitor, and recorded in the CRF. All pregnancies will be followed until resolution (*i.e.*, voluntary or spontaneous termination or birth) and assessed for congenital anomalies and birth defects.

7.3.6 Medical significance

An event that is not fatal or life-threatening and that does not necessitate hospitalization may be considered serious if, in the opinion of the investigator, it jeopardizes the patient's status and might lead to medical or surgical intervention to prevent any of the above outcomes. Such medically significant events could include allergic bronchospasm requiring intensive treatment in the emergency room or at home, blood dyscrasias that do not result in inpatient hospitalization, or the development of drug dependency or abuse.

7.4 Perioperative Adverse Events

Complications of surgery or those occurring in the early post-operative period will be recorded. These include wound complications, estimated blood loss, post-operative infections, delayed wound healing, abnormal laboratory values, etc. Duration of hospital stay will be recorded. Additional medical examinations will be allowed at the request of patients during drug administration or at the discretion of the principal investigator for the evaluation of new adverse events that warrant physical examination. During and following completion of the study, patients should notify the study staff of any problems that occur between visits or following study termination by telephone and, if necessary, will be evaluated by the investigator or study personnel at an unscheduled interim visit.

Operative/perioperative events will be recorded as described in Section 7.1, and their severities will be categorized using the NCI CTCAE version 4.0 criteria. The relationship of these events to the investigational drug(s) will be determined by the principal investigator together with urologist co-investigators and, if necessary, with the primary urologic surgeon. Reporting of these events will follow the same guidelines described in Section 7.5.

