> We aim (Primary Outcome) to investigate whether inhibition of M2-TAMs via administration of dupliumab, an IL4 receptor antagonist approved for use in topic dermatitis, will inhibit the infiltration of M2-TAMs in primary prostate cancers in the neoadjuvant setting for men with localized high-risk prostate cancer (11, 12). This will be accomplished by a comparison of pre-dupilumab M2-TAM infiltration in the biopsy vs. post-dupilumab M2-TAM infiltration in the RP specimen. Secondary outcomes will include: 1) confirmation of the safety and feasibility of Dupilumab administered using a standard dose / schedule in the neo-adjuvant setting; 2) Quantify the extent of CD8+ T cell infiltration into the prostate from harvested prostate glands of treated patients; 3) Quantify the extent of CD4+ T cell and Treg infiltration into the prostate in prostate specimens of treated patients; 4) Quantify markers of apoptosis in prostate tumor specimens of treated patients using TUNEL staining and expressed as the mean staining percentage in tumor tissue; 5) Quantify markers of cell proliferation in prostate tumor specimens of treated patients using Ki-67 staining and expressed by the mean staining percentage in tumor; 6) Evaluate the proportion of pathological complete responses in prostate tumor specimens of treated patients; 7) Evaluate PSA response rates defined as the proportion of patients who achieve an undetectable PSA (<0.1 ng/mL) by 3 months after prostatectomy. We hypothesize that neoadjuvant Dupilumab will be feasible and safe (i.e. will not interfere with subsequent prostatectomy), and will produce a measurable decrease in M2-TAM infiltration into the primary tumor microenvironment.

If this study shows significant reduction in M2-TAM infiltration and administration of the study drug is feasible and safe, then future studies would aim to use Dupilumab in the mCRPC setting as an adjunct to cytotoxic and immunologic therapies.

Objectives Primary:

• Evaluate the ability of dupilumab to inhibit M2-TAMs infiltration of prostate cancer by comparison of pre-dupilumab M2-TAM infiltration in the biopsy vs. post-

dupilumab M2-TAM infiltration in the RP specimen.

Secondary:

- To confirm the safety and feasibility of Dupilumab administered using a standard dose / schedule in the neo-adjuvant setting
- Quantify the extent of CD8+ T cell infiltration into the prostate from harvested prostate glands of treated patients

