1.2 Secondary Objectives

- To evaluate the safety and tolerability of DUPILUMAB administered 600 mg s.q. on day 1, and then 300 mg s.q. on days 8,15, 22, 29, 36, 43. They will then undergo surgery on day 56.
- To evaluate the feasibility of administering DUPILUMAB administered 600 mg s.q. on day 1, and then 300 mg s.q. on days 8,15, 22, 29, 36, 43.
- Quantify the extent of CD8+ T cell infiltration into the prostate from harvested prostate glands of treated patients
- Quantify the extent of CD4+ T cell and Treg infiltration into the prostate in prostate specimens of treated patients
- Quantify markers of apoptosis in prostate tumor specimens of treated patients using TUNEL staining and expressed as the mean staining percentage in tumor tissue
- Quantify markers of cell proliferation in prostate tumor specimens of treated patients using Ki-67 staining and expressed by the mean staining percentage in tumor
- Evaluate the proportion of pathological complete responses in prostate tumor specimens of treated patients
- Evaluate PSA response rates defined as the proportion of patients who achieve an undetectable PSA (<0.1 ng/mL) by 2 months after prostatectomy.

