Power. For the primary outcome of pre- vs. post-treatment decrease in M2-TAM infiltration, power is based on the paired t-test. With 20 patients, we have the power (\geq 81%) to detect a decrease of \geq 0.67 standard deviation unit (effect size = 0.67) (14). This is likely to be conservative as we observed a much larger difference in M2-TAM levels between primary and metastatic tumors in our data. Power calculated using PASS v. 11 (NCSS Software, Kaysville, UT). The continuous toxicity monitoring design with n=20 above has probability = 0.048 of early stopping if the Grade \geq 3 AE rate is <15%. Toxicity boundaries calculated using software developed by Ivanova (13)

(http://cancer.unc.edu/biostatistics/program/ivanova/ContinuosMonitoringForToxicity.aspx)

Frequency, types, and grades of adverse events in each treatment group will be measured using the NCI Common Toxicity Criteria version 4.0, and will be summarized using descriptive statistics. Formal safety assessments will be performed from the time of first administration Dupilumab until the 60th postoperative day.

10.1.2: **Early stopping rule for feasibility:** We do not anticipate an increase in the surgical difficulty with the use of neoadjuvant DUPILUMAB. Men who have had acute (post-biopsy) and prolonged issues (chronic prostatitis) with prostate infection/inflammation are fairly routine in urologic surgical practice, and we anticipate that the immune infiltrate potentially induced by DUPILUMAB would not pose a substantial increase in surgical difficulties. However, in addition to safety, feasibility will be monitored separately. The feasibility rule for this study will be based on a change in surgical outcomes beyond what may be expected for patients without presurgical interventions and that may be attributable to the study drug. These events would include: (1) average blood loss in excess of 2500 mL, (2) average operative time in excess of 3.5 hours, and (3) average hospital stay in excess of 4 days. These values are

approximately 2 standard deviations above the average surgical outcomes for men undergoing radical prostatectomy at Johns Hopkins Hospital.

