10.4 Safety Analysis

10.4.1 Evaluation of adverse events

Treatment-emergent adverse events will be translated from investigator terms to MedDRA version 6.0 terminology and summarized (number and percentage of patients) for all patients who receive at least one dose of the study drug(s). Adverse event summaries will be organized by body system, frequency of occurrence, intensity (*i.e.*, severity grade), and causality or attribution. Patients who experience an adverse event more than once will be counted only once. The occurrence with the maximum severity will be used to calculate intensity.

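### Non-interference with prostatectomy is hypothesised, but blood loss, operative time and hospital stay get no final estimate: as quantities they enter only a stopping rule with cuts about 2 SD above average

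*Combined protocol and SAP*

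**What the plan says.** - **Hypothesis and objective.** The synopsis rationale expects neoadjuvant dupilumab to be safe and feasible in the sense that it "will not interfere with subsequent prostatectomy". It makes later studies in metastatic disease conditional on feasibility and safety. Section 1.2 includes "To evaluate the feasibility of administering DUPILUMAB" among the secondary objectives.
- **Data recorded.** Section 7.4 lists what is captured around surgery: "These include wound complications, estimated blood loss, post-operative infections, delayed wound healing, abnormal laboratory values, etc. Duration of hospital stay will be recorded". Operative time is not named there. For operative and perioperative events, "their severities will be categorized using the NCI CTCAE version 4.0 criteria", and their relation to the drug is judged.
- **Feasibility rule.** Section 10.1.2 describes a rule "based on a change in surgical outcomes beyond what may be expected for patients without presurgical interventions". It sets limits of 2500 mL for blood loss, 3.5 hours for operative time and 4 days for hospital stay, each worded as an average. The limits are said to lie "approximately 2 standard deviations above the average surgical outcomes for men undergoing radical prostatectomy at Johns Hopkins Hospital". The average and SD themselves are not printed. The rule uses a Beta(9,1) prior and suspends the study when the posterior probability that the complication-free rate is below 0.90 exceeds 80%. A printed list of stopping counts follows, ending at 8 of 16.
- **Analyses.** Sections 8.3 and 10.2.2 contain no surgical or feasibility endpoint. In Section 10.4.1, "Adverse event summaries will be organized by body system, frequency of occurrence, intensity" and attribution. Section 10.4.2 summarises serious events separately. Section 10.5.1 promises descriptive statistics for most study outcomes without saying which.

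**The concern.** In a single-arm study, surgical burden is one of the few safety questions for which the investigators evidently have an in-house reference, since the limits were set from it. The plan turns that information into a count of men beyond a distant limit and plans no estimate of how far the measures moved. A cut at 2 SD is insensitive to a moderate shift in the mean: most men whose operation was somewhat longer or bloodier stay below it. At the end of the study, the feasibility objective would have a stopping rule and a table of graded adverse events, but nothing stating by how much blood loss, operative time or stay differed from usual, or with what uncertainty. Since later studies depend on the feasibility finding, a moderate worsening could go unquantified although the data to describe it exist.

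**Working it through.** **1. The plan's own figures.** With x complications in n men the posterior is Beta(9 + n − x, 1 + x). The criterion is P(complication-free rate < 0.90) > 0.80.

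- 2 of 2, 2 of 3 and 2 of 4 give 0.910, 0.889 and 0.866. The list agrees with the criterion.
- 2 of 6, Beta(13,3), gives 0.816, so the criterion is already met. The list asks for 3 of 6 (0.944).
- The criterion requires 2 at n = 5–6, 3 at n = 7–14 and 4 at n = 15–20. The list rises to 8 of 16 and then ends, with 20 men planned.

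The list is therefore not reproduced from n = 6, and both versions are carried below. As a check on the method, the same exact binomial recursion applied to the toxicity boundary at a 15% event rate gives 0.04796, against the plan's 0.048.

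**2. Assumptions not in the documents.** Each measure is normal with SD unchanged by treatment; the cut is exactly 2 SD above the average; events are counted per man; every exceedance counts as attributable; the reference mean is fixed. All 20 men reach surgery, in line with the synopsis definition of evaluable.

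**3. One measure.** The chance that a man exceeds the cut is P(Z > 2 − shift). Stopping probabilities come from the recursion to n = 20. The last column is the upper-side power of a two-sided 5% one-sample t comparison (noncentral t, 19 df, noncentrality shift × √20). It serves only as a gauge of how much information a mean carries.

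| Shift (SD) | Exceedance | Printed list | Posterior criterion | Mean vs average |
|---|---|---|---|---|
| 0.5 | 6.7% | 2.6% | 10% | 56% |
| 0.75 | 10.6% | 6.2% | 26% | 89% |
| 1 | 15.9% | 13.5% | 51% | 99% |

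The false-signal rates are not equal. With no shift, exceedance is 2.3% and the list and criterion trigger in 0.3% and 1.0% of trials, against 5% (two-sided) for the comparison of means. Part of the gap reflects that stricter setting.

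**4. Three measures, any exceedance counts (simulated).**

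| 1-SD shift in | Correlation | Event rate | Printed list | Posterior criterion |
|---|---|---|---|---|
| one of three | about 1 to 0 | 16–20% | 13–20% | 51–67% |
| all three | 0.5 | 32% | 48% | 95% |
| all three | about 1 to 0 | 16–40% | 15–67% | 54–99% |

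**5. Limits read literally as averages.** With one measure shifted by 1 SD, the running average passes the cut at some look from the second man onward in about 10% of trials. At n = 20 the probability is P(Z > √20 = 4.47), about 4 in a million.

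**6. What an interval would give.** The half-width is t(0.975, 19)/√20 = 2.093/4.472 = 0.468 SD. A 1-SD shift is separated from the average with about 99% probability for one measure, or 96% with Bonferroni over three. With only 16 operated men, the half-width is 0.53 SD and the single-measure probability 96%.

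**The case against.** **The measures are not ignored elsewhere.** Section 7.4 names blood loss among the perioperative events to be graded and attributed, and Section 10.4.1 summarises adverse events. Prolonged hospitalisation is a seriousness criterion (Sections 7.3 and 7.3.3), with a narrative under Section 10.4.2. This stands: a reader might infer that the stopping rule is the only planned use of these data, and the documents do not support that. What remains is narrower. Those uses are counts of graded events, operative time is not named in Section 7.4, and the general promise in Section 10.5.1 neither identifies these measures nor offers a comparison with the average.

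**A 1-SD worsening need not pass unnoticed.** A reader might infer that such a trial would usually be reported as feasible. That fits the printed list with one measure shifted (80–87% not stopped). It fails under the written criterion, which suspends in 51–99% of trials, and is about even under the list when all three shift at correlation 0.5 (52% not stopped). Crossing the rule also leads only to suspension for review; nothing makes the final conclusion depend on the rule alone.

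**The reference is not like for like.** It describes men having prostatectomy at the hospital generally, whereas the trial enrols high-risk men. If case mix alone moved a mean by 0.25 or 0.5 SD (assumed), a formal one-sample test would signal worsening in 18% or 56% of trials with no drug effect. This stands, and rules out a formal test as the basis for a conclusion. It does not count against a labelled estimate with its interval.

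**Conclusion.** The point holds in a limited form. Surgical non-interference is hypothesised and feasibility is an objective, but no final estimate of blood loss, operative time or hospital stay is planned. As quantities they enter only through limits about 2 SD above the institutional average. Under the stated assumptions, a 1-SD worsening in one measure triggers the printed list in about 13.5% of trials and the written criterion in about 51%; with all three shifted at correlation 0.5, about 48% and 95%. Requiring attribution to the drug would lower all these figures. An interval of about ±0.47 SD would say directly what the rule can only hint at. The normality, correlation and fixed-reference assumptions are not from the documents, and skewed data would change the exact values. The probability of showing a shift from the historical average is not a probability of showing a drug effect. This is an inexpensive and worthwhile reporting gap to close; it does not invalidate the rule's monitoring role or the primary analysis.

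**What to change.** 1. Leave the rule in its monitoring role and add to Section 10.4 or 10.2.2 a final descriptive analysis. Give the mean (log-scale mean or median if skewed) and 95% CI for each of the three measures, beside the institutional average and SD.
2. Print that average and SD in Section 10.1.2, and state in Section 7.4 that operative time is recorded.
3. Label the display as a historical comparison subject to case mix, with no formal test as the basis for a conclusion. Have the feasibility conclusion cite these intervals as well as the rule.
4. Separately, reconcile three elements of Section 10.1.2: the posterior criterion, the printed list (they disagree from n = 6, and the list ends at 16 of 20 men), and limits worded as averages but applied as counts of men. Which reading governs is for the sponsor to settle.

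The cost of items 1–3 is about one paragraph of analysis text, one recorded variable to confirm and a few institutional figures to print. The drawback is that a less favourable surgical picture might have to be reported and explained against an imperfect reference.

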7.5 Reporting Adverse Events

7.5.1 Reporting serious adverse events (SAEs)

All SAEs and unknown/unexpected reactions should be reported to the PI within 24 hours.

The lead study coordinator, [name] should be contacted when reporting an SAE or death at [contact] and [contact] If this person cannot be reached within 24 hours, the PI should be contacted at [contact] or at [contact]. The initial report for each SAE or death should include the following information (see also Appendix C for SAE Reporting Form):

- protocol # and title
- patient initials, study identification number, sex, age
- date the event occurred
- description of the SAE
- investigational agent received (and dose level) at the time the SAE occurred
- description of the patient's condition
- indication of whether the patient remains on study

Follow-up information including severity, causality, action taken, concomitant medications, and outcome should be communicated to the principal investigator and study coordinator as soon as possible with an indication whether an amendment will need to be made to the protocol, the consent form, or both, as a result of this event.

7.5.2 Reporting requirements for the Sidney Kimmel Comprehensive Cancer Center (SKCCC)

The principal investigator will notify the appropriate regulatory agencies of any SAEs occurring during the study period, regardless of causality. These agencies include the Sidney Kimmel Comprehensive Cancer Center (SKCCC) Data and Safety Monitoring Committee (DSMC), and the Institutional Review Board (IRB) and the Institutional Biosafety Committee (IBC) of the Johns Hopkins Medical Institutions (JHMI). For SAEs that are fatal, life-threatening, or treatment-related but non-life threatening: IRB/IBC reporting by the PI is required within 3 days. For unrelated SAEs, IRB/IBC reporting by the PI is required within 15 days. All other AEs should be documented on CRFs and submitted according to the standard data management guidelines.

Adverse event information will be collected continuously throughout the duration of the study. Participants will be instructed to notify their treating provider of any new signs or symptoms, and providers will actively assess patients for adverse events at each visit (including by evaluation of laboratory studies). The investigator will assess each AE for its severity and for its relationship to the study drug, and all events Grade 1 or higher will be documented on CRFs and then reported as described above within the required time frame. Any AE occurring while a patient is on study (*i.e.* after informed consent has been signed) or within 30 days of study termination requires reporting. AEs occurring later than

this must still be reported if a causal relationship with the study drug is suspected.

For all AEs, the investigator must pursue and obtain information to adequately determine the causality and outcome of the event, and to assess whether it meets criteria for a SAE. In addition, follow-up of an AE is required until the event either resolves or stabilizes. Initial reporting of an AE should include at a minimum the patient number, age, the dose at which the event occurred, and the type and severity of the event. Follow-up information including causality, duration, outcome, action taken, and concomitant medications should be reported soon thereafter.

The principal investigator must keep copies of all CRFs and other AE information, including correspondence with the IRB for as long as required to comply with national and international regulations (generally at least 3 years after study completion).

7.5.3 Research Involving).

